#### **6.4 Protocol Therapy Discontinuation**

In addition to discontinuation from therapy related to toxicities as outlined above, a subject will also be discontinued from protocol therapy and followed per protocol under the following circumstances outlined below. The reason for discontinuation of protocol therapy will be documented on the electronic case report form (eCRF)

- Completion of maximum of 35 cycles of study treatment.
- Documented disease progression per RECIST 1.1 (subjects with measurable disease) or PCWG (subjects without measurable disease). If a subject is receiving clinical benefit (as determined by treating physician), treatment can continue after discussion with sponsor-investigator.
- Site investigator determines a change of therapy would be in the best interest of the subject
- Subject requests to discontinue protocol therapy, whether due to unacceptable toxicity or for other reasons
  - In a subject decides to prematurely discontinue protocol therapy (“refuses treatment”), the subject should be asked if he or she may still be contacted for further scheduled study assessments. The outcome of that discussion should be documented in both the medical records and in the eCRF.
- If protocol therapy (both drugs) is interrupted for  $\geq 42$  days from the expected day of the next treatment. If one drug is permanently discontinued, treatment with the other drug may continue at investigator discretion.

#### **6.5 Protocol Discontinuation**

If a subject decides to discontinue from the protocol (and not just from protocol therapy) all efforts should be made to complete and report study assessments as thoroughly as possible. A complete final evaluation at the time of the subject's protocol withdrawal should be made with an explanation of why the subject is withdrawing from the protocol. If the reason for removal of a subject from the study is an adverse event, it will be recorded on the eCRF.

#### **6.6 Safety Follow Up**

The safety follow-up visit should only occur when subjects permanently stop study treatment for whatever reasons (toxicity, progression, or other reason) and should be performed 30 days (+ 7 days) after the last dose of treatment. Participants with an AE of Grade  $> 1$  will be followed until the resolution of the AE to Grade 0-1 or until the beginning of a new anti-cancer therapy, whichever occurs first. SAEs that occur within 90 days of the end of treatment or before initiation of a new anti-cancer treatment should also be followed and recorded. The Day 90 assessment may be performed via phone call, email or other avenues as appropriate.

#### **6.7 Long Term Follow Up**

For subjects who discontinue for reasons other than progressive disease, radiographic disease assessment should be performed per discretion of the site investigator per standard of care for disease assessment. The scan interval may be reset if scans were done sooner for clinical reasons and the type of scan may be left to discretion of the site investigator. This imaging may be done locally. Follow up for these subjects will occur every 6 months until progression. Once disease progression is documented, subjects will be followed for survival every 6 months for 5 years from the time of documented progression. Follow up may be accomplished via clinic visit, phone

call, or other avenues as appropriate. A window of  $\pm$  14 days will be applied to long term follow up.

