4: Chromogranin A, neuron specific enolase and urine NTx (optional) will be performed at screening/day 1 then prior to treatment every other Cycle starting at Cycle 3 Day 1 then at the D30 safety visit. PSA should be obtained at screening then prior to treatment every Cycle then at the D30 safety visit. Subjects that come off study without progression should have PSA obtained per investigator discretion. Testosterone will be performed at screening and at the D30 safety visit.

5: Tumor response assessment will consist of evaluation by CT scans of chest and MRI or CT of abdomen and pelvis. If a PET/CT is done for tumor assessment and if tumor/s are visible on the CT, this may be used for tumor evaluation. A bone scan will be obtained at screening and with other radiology imaging at the frequency as outlined below. An MRI of the brain should be performed at screening if there is a concern for the presence of brain metastases. Tumor imaging will be done at screening and every 3 cycles (9 weeks) for the first 12 cycles (36 weeks) and then every 4 cycles (12 weeks) until the patient is off study therapy (window of  $\pm$  1 week). Tumor imaging should follow week intervals in the case of study treatment delays due to toxicities. During follow up after completion of study treatment, imaging frequency is at the discretion of the site investigator. Imaging selected for each subject should remain the same throughout the study. Tumor imaging to be done at treatment discontinuation/safety follow up visit is at discretion of site investigator. If tumor assessments are available for subjects who have not yet experienced progressive disease (PD) at the time treatment is discontinued, the follow-up tumor evaluations will be documented in the eCRF until PD or death is confirmed, or until another treatment is initiated.

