8: Safety Follow Up: The safety follow-up visit should only occur when subjects permanently stop study treatment for whatever reasons (toxicity, progression, or other reason) and should be performed 30 days (+ 7 days) after the last dose of treatment. Participants with an AE of Grade > 1 will be followed until the resolution of the AE to Grade 0-1 or until the beginning of a new anti-cancer therapy, whichever occurs first. SAEs that occur within 90 days of the end of treatment or before initiation of a new anti-cancer treatment should also be followed and recorded. The Day 90 assessment may be performed via phone call, email or other avenues as appropriate.

9: Long Term Follow Up: For subjects who discontinue for reasons other than progressive disease, radiographic disease assessment should be performed per discretion of the site investigator per standard of care for disease assessment. The scan interval may be reset if scans were done sooner for clinical reasons and the type of scan may be left to discretion of the site investigator. This imaging may be done locally. Follow up for these subjects will occur every 6 months until progression. Once disease progression is documented, subjects will be followed for survival every 6 months for 5 years from the time of documented progression. Follow up may be accomplished via clinic visit, phone call, or other avenues as appropriate. A window of  $\pm$  14 days will be applied to long term follow up.

10: Screening labs as outlined in Section 3 of the inclusion criteria must be performed within 10 days of C1D1. If screening (baseline) CBC and CMP were performed within 7 days of Day 1 of treatment, these do not need to be repeated. All laboratory assessments should be done prior to treatment.

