### 9.8.2 Radiologic Progression Free Survival (rPFS)

rPFS has two components to its definition. For soft tissue lesions, rPFS will be measured from Cycle 1 Day 1 to date of radiologic progression per RECIST 1.1 or death from any cause, whichever occurs first. For bone lesions (non-measurable disease), rPFS will be measured from Cycle 1 Day 1 to date of progression per PCWG3 criteria [9] or death from any cause, whichever occurs first. Thus, the “date of progression” is the earlier date of either of those two possible types of progression. Subjects who have not progressed will be right-censored at the date of the last disease evaluation.

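### After a patient stops treatment without progression, the protocol lets the site change the type of scan, and the rPFS rules do not require that both soft tissue and bone were assessed

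*Combined protocol and SAP*

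**What the plan says.** **Endpoint.** Section 9.8.2 gives rPFS two parts. The first reads "For soft tissue lesions, rPFS will be measured from Cycle 1 Day 1 to date of radiologic progression per RECIST 1.1 or death"; a parallel rule covers bone lesions under PCWG3. The progression date is the "earlier date of either of those two possible types of progression". Patients without progression are censored at their last disease evaluation, and the section does not say what that evaluation must include. Section 12.3 counts a success as at least 6.00 months of rPFS. Section 12.6 makes a patient evaluable after one cycle plus radiology imaging, with no modality named.

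**On treatment.** Footnote 5 to the Section 7 calendar schedules CT/MRI every 9 weeks for 36 weeks and every 12 weeks thereafter. Bone imaging goes with it: "A bone scan will be obtained at screening and with other radiology imaging at the frequency as outlined below". It also states: "Imaging selected for each subject should remain the same throughout the study".

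**After treatment.** Footnote 5 relaxes the timing only: "During follow up after completion of study treatment, imaging frequency is at the discretion of the site investigator". It adds "If tumor assessments are available for subjects who have not yet experienced progressive disease (PD) at the time treatment is discontinued", those evaluations are to be entered in the eCRF. For patients who stop for reasons other than progression, Section 6.7 says that "the type of scan may be left to discretion of the site investigator". Footnote 9 carries the same wording. Section 12.7 also leaves these patients' disease assessment to the investigator. The calendar table marks CT chest, CT or MRI of abdomen and pelvis, brain MRI and bone scan in the long-term follow-up column.

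**The concern.** A composite of two progression types is observed only if both are looked for. On treatment they are looked for together, on fixed dates and with a stable modality. Once a patient stops without progression, one rule asks for the same imaging and another frees the choice of scan. A site that follows the second can image one component and still generate an evaluation date that counts for the whole composite.

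That off-treatment time enters the same Kaplan-Meier curve and the same yes/no 6-month endpoint as fully imaged time. If progression in the unimaged component is missed or found late, rPFS is overstated, and the result comes to depend partly on how many patients leave treatment early for toxicity or by choice. A fixed off-treatment scan interval would not cure this, because the question is what is imaged rather than when.

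**Working it through.** **1. The rules side by side, for a patient off treatment without progression**

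| Place | Frequency | Type of scan |
|---|---|---|
| Footnote 5 | site's choice | should stay the same |
| Section 6.7 and footnote 9 | per standard of care, site's choice | may be the site's choice |
| Calendar table, long-term column | marked | CT/MRI and bone scan both marked |
| Section 12.7 | investigator's choice | not stated |

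The table does not settle the matter. Its imaging marks carry footnote 5 and its column header carries footnote 9, so a site can cite either.

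**2. Path to the endpoint**

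Take invented dates. A patient has clear CT and bone scans at week 9, stops for toxicity at week 15, and has a clear CT without a bone scan at week 30.

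- Six months is 6 × (365.25/12)/7 = 26.09 weeks.
- Under 9.8.2 as written, censoring is at week 30. Since 30 > 26.09, the patient can be counted as a success under 12.3.
- Bone was last formally assessed at week 9, which is 30 − 9 = 21 weeks earlier.
- If the last evaluation had to cover both components, censoring would be at week 9 and success at 6 months would not be shown.

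Neither 12.3, 12.4.1 nor 12.6 says how such a patient is classified. A patient who stops after month 6 with both components already clear at or after that date affects only the Kaplan-Meier estimate.

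**3. The plan's own design figures**

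Inputs from Section 12.3: n1 = 27, r1 = 2, n = 40, r = 6, p0 = 0.10, p1 = 0.25.

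- PET = P(X1 ≤ 2 | 27, 0.10) = 0.4846 (plan: 0.485).
- ASN = 27 + (1 − 0.4846) × 13 = 33.70 (plan: 33.70).
- P(promising | p) = Σ over x ≥ 3 of P(X1 = x) × P(X2 ≥ 7 − x), with X2 binomial on 13 patients. This gives 0.0977 at p = 0.10 and 0.9001 at p = 0.25, against the stated 0.125 and 0.90.
- Enrolment: 40/(1 − 0.20) = 50.

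The design is correctly computed.

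**4. How sensitive the decision rule is to any upward shift**

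This is an illustration on assumptions, because the documents give neither quantity needed. Let f be the share of true 6-month failures who stop without progression before month 6. Let m be the probability that such a failure is then counted as a success because one component was not imaged. The apparent null rate is 0.10 + 0.90 × f × m.

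| f | m | Apparent rate | P(promising) when the true rate is 0.10 |
|---|---|---|---|
| 0 | – | 0.1000 | 0.098 |
| 5% | 10% | 0.1045 | 0.117 |
| 10% | 10% | 0.1090 | 0.137 |
| 10% | 25% | 0.1225 | 0.209 |
| 20% | 25% | 0.1450 | 0.354 |

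The 0.125 ceiling is reached at an apparent rate of 0.1064, that is 40 × 0.0064 = 0.26 extra apparent successes per 40 patients. These rows describe the Simon rule under chosen inputs; they do not estimate the effect of this gap.

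**The case against.** The strongest reply is that the calendar still lists CT/MRI and bone scan in long-term follow-up. Read with that column, freedom over the type of scan could mean CT versus MRI, or PET/CT, and not permission to omit bone imaging. Footnote 5 says should rather than must, and Section 6.7 can be read as a specific exception to a general rule. This stands to the extent that loss of a component is allowed by the text but not certain. It does not remove the ambiguity, since a site following CT alone could point to 6.7.

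A reader might infer that CT-only follow-up gives no look at bone. That goes too far. CT of chest, abdomen and pelvis shows part of the skeleton, and Sections 9.6 and 9.7 count any new lesion, or unequivocal non-target progression, as progressive disease. CT alone is less complete than CT plus bone scan, but it is not blind to bone. Death also counts in either case.

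A reader might also multiply assumed shares, say 10–30% stopping without progression and 20–40% of progressions in bone only, to get 40 × 0.10 × 0.20 = 0.8 to 40 × 0.30 × 0.40 = 4.8 patients. The documents support neither range. The product also takes every such patient to progress, at any time, under CT-only follow-up that never shows bone disease. It is not a count of wrong 6-month successes.

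Three further points stand:

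- A switch to a more sensitive modality could bring progression forward, so the bias is not upward in every case.
- Section 6.4 lets one drug continue after the other is stopped; such patients remain on scheduled imaging, which narrows the exposed group.
- Off-treatment scan timing is also discretionary and may matter more than scan type. That is a separate gap and does not close this one.

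**Conclusion.** The point holds as an unresolved inconsistency with a permitted gap in ascertaining the primary endpoint. Footnote 5 on one side, and 6.7 with footnote 9 on the other, should be reconciled. Section 9.8.2 lets an evaluation of one component stand for both.

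The likely direction is upward, through missed or late progression in the component not imaged. The size cannot be derived from the documents. The binary endpoint is affected only for a patient who stops without progression before month 6, truly progresses before month 6 in the component not imaged, and still has a scan at or after month 6 that looks progression-free. Later stops bear on the Kaplan-Meier rPFS only.

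The documents do not support a claim that type I error is inflated to any particular value, or that bone progression will go unseen. They show that the rule has little slack: about a quarter of one extra apparent success per 40 patients takes it past 0.125. That is reason enough for an inexpensive correction of wording. The Simon design itself needs no change on this account.

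**What to change.** 1. **Section 6.7 and footnote 9.** Remove only the clause "the type of scan may be left to discretion of the site investigator" and keep the clause on resetting the scan interval. State that off-treatment assessments used for rPFS repeat that subject's baseline modalities, CT/MRI plus bone scan, as the calendar already marks. Align Section 12.7 with this.
2. **Section 9.8.2.** Define the last disease evaluation, for censoring, as the last date on which both soft tissue and bone were assessed. Progression seen on any scan still counts as an event on its own date.
3. **Sections 12.3 and 12.4.1.** State that a subject is a 6-month success only if both components were assessed as progression-free at or after month 6.

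One detail needs settling with item 3. The scheduled week-27 scan has a window of ±1 week, so it can fall at week 26, just short of 26.09 weeks. The plan should say whether such a scan satisfies the rule.

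**Cost.** The changes are to wording in the protocol and statistical section. Sites lose some freedom after treatment and may have to add bone scans. Single-component assessments stop extending rPFS, so some patients are censored slightly earlier, and the observed 6-month success rate may be slightly lower.

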## 7. STUDY CALENDAR & EVALUATIONS

Study Evaluation Cycle = 21 days	Screening 	Cycle 1	Cycle 2+	Safety follow up visit 	Long-term Follow up 
	-28 days from C1D1	Day 1 ± 3 days	Day 1 ± 3 days	30/90 days post last dose + 7 days	Every 6 months (±14 days)
REQUIRED ASSESSMENTS					
Informed Consent	X				
Medical History and Disease Staging 	X				
Physical Exam	X	X	X	D30	
Vital signs and ECOG Performance Status 	X	X 	X 	D30	
ECG 	X	X 	X 		
AEs & concomitant medications	X	X	X	X	
LABORATORY ASSESSMENTS					
Complete Blood Cell Count with diff (CBC) 	X	X 	X	D30	
Comprehensive Metabolic Profile (CMP) 	X	X 	X 	D30	
PT/INR and aPTT 	X				
Thyroid Function Testing 	X		X 		
Urine protein 	X		X 		
Chromogranin A, neuron specific enolase and urine NTx 	X		X 	D30	
Prostate-specific antigen (PSA) 	X		X	D30	X 
Testosterone 	X			D30	
DISEASE ASSESSMENT					
CT of chest 	X		X 	D30 	X 
CT or MRI of abdomen and pelvis 	X		X 	D30 	X 
MRI Brain 	X		X 	D30 	X 
Bone scan 	X		X 	D30 	X 
TREATMENT EXPOSURE					
Lenvatinib		D1-21	D1-21		
Pembrolizumab		X	X		
SPECIMEN COLLECTION					
Archival Tumor Tissue 	X 				
Blood for somatic baseline		X			
Blood for plasma 		X 		D30 	
Stool for microbiome 		X 			
FOLLOW-UP					
Survival Status, Subsequent Therapy					X

## Key to Footnotes

1: Medical History; other data to obtain during this assessment includes a smoking history questionnaire and trial awareness question. In addition, prior anti-cancer treatment should be documented including medications (chemotherapy, checkpoint inhibitors, etc) radiation or surgery. Prior genomic sequencing and PD-L1 results are required if available. Diagnosis and staging to include pathology report and imaging reports.

2: Vital signs to include temperature, pulse, respirations, blood pressure, weight, and height (screening only) and ECOG performance status. Blood pressure should be monitored after 1 week of treatment with lenvatinib (around C1D7), then every 2 weeks for the first 2 months (C2D1 at clinic visit and C2D14) and Day 1 of every cycle thereafter while on treatment. If a subject develops systolic BP  $\geq$  140 mmHg or diastolic BP  $\geq$  90 mmHg active management is indicated. Monitoring may be done locally by clinic visit, at home BP monitoring or similar. Subjects will be asked to maintain a record of BP readings and communicate results to research staff at timepoints as outlined above. ECG to be performed at screening then as clinically indicated during study treatment per investigator discretion.

3: CBC with differential and platelet to include: WBC, ANC, Hgb, Hct, PLT. CMP to include sodium, potassium, chloride, creatinine, blood urea nitrogen; calcium, albumin, and liver function tests (LFTs). LFTs to include AST, ALT, total bilirubin, and alkaline phosphatase; LFTs will be monitored every 2 weeks for 2 months (C1D14, C2D1, C2D14, C3D1). PT/INR and PTT should be obtained at screening then at site investigator discretion. Thyroid Function testing should be performed at screening then every 4 cycles (12 weeks). TSH should be obtained. T4 and T3 including free versus total testing is at the discretion of the site investigator. Urine protein should be obtained at screening then every 3 cycles (9 weeks). If urine dipstick  $\geq$  2+ is detected, dose interruptions, adjustments, or discontinuation may be necessary.

4: Chromogranin A, neuron specific enolase and urine NTx (optional) will be performed at screening/day 1 then prior to treatment every other Cycle starting at Cycle 3 Day 1 then at the D30 safety visit. PSA should be obtained at screening then prior to treatment every Cycle then at the D30 safety visit. Subjects that come off study without progression should have PSA obtained per investigator discretion. Testosterone will be performed at screening and at the D30 safety visit.

5: Tumor response assessment will consist of evaluation by CT scans of chest and MRI or CT of abdomen and pelvis. If a PET/CT is done for tumor assessment and if tumor/s are visible on the CT, this may be used for tumor evaluation. A bone scan will be obtained at screening and with other radiology imaging at the frequency as outlined below. An MRI of the brain should be performed at screening if there is a concern for the presence of brain metastases. Tumor imaging will be done at screening and every 3 cycles (9 weeks) for the first 12 cycles (36 weeks) and then every 4 cycles (12 weeks) until the patient is off study therapy (window of  $\pm$  1 week). Tumor imaging should follow week intervals in the case of study treatment delays due to toxicities. During follow up after completion of study treatment, imaging frequency is at the discretion of the site investigator. Imaging selected for each subject should remain the same throughout the study. Tumor imaging to be done at treatment discontinuation/safety follow up visit is at discretion of site investigator. If tumor assessments are available for subjects who have not yet experienced progressive disease (PD) at the time treatment is discontinued, the follow-up tumor evaluations will be documented in the eCRF until PD or death is confirmed, or until another treatment is initiated.

6: Archival tissue obtained within 12 months of registration is required if available. Archival tissue should be identified at screening and shipped prior to Cycle 2 Day 1 treatment. If not available, the patient may still be eligible after discussion with the sponsor-investigator. These samples will be stored for correlative analysis which may include PD-1/PD-L1 expression, tumor mutation burden, and next generation sequencing to evaluate genomic markers once funding is available. Subjects will also be consented for optional storage of any remaining tissue/blood samples after protocol-specified studies are complete. These samples will be stored for future unspecified cancer-related research and are considered “banking samples”. See Correlative Laboratory Manual (CLM) for additional details regarding correlative samples.

7: Peripheral blood samples will be collected prior to treatment (1) Cycle 1 Day 1, (2) Cycle 3 Day 1 (9 weeks) and (3) at progression. For subjects that discontinue treatment for progression, these samples may be collected at the D30 safety visit. Plasma will be stored for circulating tumor DNA (ctDNA) and miRNA analysis once funding is available. Whole blood samples will also be collected prior to treatment (1) Cycle 1 Day 1 and stored for somatic baseline testing once funding is available. Stool for microbiome will be collected prior to (1) Cycle 1 Day 1 treatment and stored for correlative analysis once funding is available. Subjects will be provided instructions after consent during screening and asked to bring the sample back prior to C1D1 treatment. Subjects will also be consented for optional storage of any remaining tissue/blood/stool samples after protocol-specified studies are complete. These samples will be stored for future unspecified cancer-related research and are considered “banking samples”. See Correlative Laboratory Manual (CLM) for additional details regarding correlative samples.

8: Safety Follow Up: The safety follow-up visit should only occur when subjects permanently stop study treatment for whatever reasons (toxicity, progression, or other reason) and should be performed 30 days (+ 7 days) after the last dose of treatment. Participants with an AE of Grade > 1 will be followed until the resolution of the AE to Grade 0-1 or until the beginning of a new anti-cancer therapy, whichever occurs first. SAEs that occur within 90 days of the end of treatment or before initiation of a new anti-cancer treatment should also be followed and recorded. The Day 90 assessment may be performed via phone call, email or other avenues as appropriate.

9: Long Term Follow Up: For subjects who discontinue for reasons other than progressive disease, radiographic disease assessment should be performed per discretion of the site investigator per standard of care for disease assessment. The scan interval may be reset if scans were done sooner for clinical reasons and the type of scan may be left to discretion of the site investigator. This imaging may be done locally. Follow up for these subjects will occur every 6 months until progression. Once disease progression is documented, subjects will be followed for survival every 6 months for 5 years from the time of documented progression. Follow up may be accomplished via clinic visit, phone call, or other avenues as appropriate. A window of  $\pm$  14 days will be applied to long term follow up.

10: Screening labs as outlined in Section 3 of the inclusion criteria must be performed within 10 days of C1D1. If screening (baseline) CBC and CMP were performed within 7 days of Day 1 of treatment, these do not need to be repeated. All laboratory assessments should be done prior to treatment.

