#### 1. Timing of AE onset

Since lenvatinib is dosed daily and continuously due to a relatively short half-life (28 hours), and pembrolizumab is dosed Q3W due to a long half-life, lenvatinib can be interrupted to assess whether an AE improves/resolves with dechallenge (ie, interruption of treatment) based on the following two scenarios:

- If an AE is identified during a treatment cycle (ie, between 2 pembrolizumab doses), only lenvatinib dose interruption is needed.
- If an AE is identified at the beginning of a treatment cycle, lenvatinib can be interrupted and dosing of pembrolizumab should be held.

If the subject recovers from an AE in response to lenvatinib interruption (ie, positive dechallenge), the event is more likely to be related to lenvatinib. Otherwise, after excluding other alternative explanations, an immune-related AE should be considered.

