## **11.2 Reporting**

### **11.2.1 Adverse Events**

- AEs will be recorded from time of signed informed consent until 30 days after discontinuation of study drug(s) or until a new anti-cancer treatment starts, whichever occurs first.
- AEs will be recorded regardless of whether or not they are considered related to the study drug(s).
- All AEs will be recorded in the subject's medical record and on the appropriate study specific eCRF form within the EDC system.

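### Patients who stop before week 12 have no scheduled TSH after baseline, yet count in the all-dosed hypothyroidism rate (minor)

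*Combined protocol and SAP*

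**What the plan says.** Thyroid testing is governed by Section 7, footnote 3: "Thyroid Function testing should be performed at screening then every 4 cycles (12 weeks". In the calendar, the row "Thyroid Function Testing" is marked at screening and in the Cycle 2+ column. Its safety follow-up cell is blank. CBC, CMP, chromogranin A/NSE, PSA and testosterone are all marked D30 in that column, and footnote 4 repeats this for one of them: "Testosterone will be performed at screening and at the D30 safety visit". The CMP contents listed in footnote 3 do not include TSH, and Section 6.6 adds no thyroid test.

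For imaging, footnote 5 says "Tumor imaging will be done at screening and every 3 cycles (9 weeks) for the first 12 cycles (36 weeks", with a window of one week either way. Section 6.4 lists among the reasons to stop therapy "Documented disease progression per RECIST 1.1 (subjects with measurable disease) or PCWG (subjects without measurable disease". It allows continuation for clinical benefit after discussion with the sponsor-investigator.

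On recording, Section 6.6 says the safety visit "should be performed 30 days (+ 7 days) after the last dose of treatment", and Section 11.2.1 has AEs recorded "until 30 days after discontinuation of study drug(s) or until a new anti-cancer treatment starts, whichever occurs first". The calendar marks AE review in the safety follow-up column, whose heading allows 7 extra days.

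Section 12.4.2 makes every patient with one dose toxicity-evaluable and summarises each toxicity type in that set. It has no rule for patients who were never retested.

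**The concern.** Safety is the first secondary objective. Section 1.1 quotes hypothyroidism at 43% for this combination in other tumors, and Section 6.2, Table 1 calls for replacement hormone at Grades 2 to 4. Hypothyroidism without symptoms is found only by a blood test. If many patients leave treatment before the first scheduled on-treatment test, the safety table cannot separate patients who stayed euthyroid from patients nobody tested. Both would appear as having no event, and the all-dosed rate would tend to be too low for cases that only the laboratory can detect. A treatable condition could also go unnoticed in patients leaving the study drugs.

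**Working it through.** **1. Timing.** Cycles are 21 days (Section 5).
- First on-treatment TSH: 4 × 21 = 84 days, week 12, which is Cycle 5 Day 1.
- First scan: 3 × 21 = 63 days, week 9. With the one-week window it falls at day 70 at the latest.
- The scan comes before the TSH even at the edge of its window. A patient who stops at that scan, or for any reason before day 84, has had only the screening TSH. No later test is due, because the D30 cell is blank.

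**2. How many patients this might be.** The plan gives no figure for thyroid testing or for stopping by week 9. The nearest figures are the six-month rPFS rates in Section 12.3 (p0 = 0.10, p1 = 0.25). The design built on them reproduces:
- PET is the binomial probability of at most 2 successes in 27 at p = 0.10, which is 0.4846 (plan 0.485).
- ASN = 27 + (1 − 0.4846) × 13 = 33.70 (plan 33.70).
- Power is 0.9001 (plan 0.90), and attained alpha is 0.0977 (within the 0.125 limit).

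Assume an exponential rPFS curve, with every stop a progression or death. Week 9 is 63 / 30.4375 = 2.07 months, and the share progressed or dead by then is 1 − p^(2.07/6).

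| Six-month rPFS | Event-free at week 9 | Progressed or dead | Of 50 dosed |
|---|---|---|---|
| 0.10 | 0.452 | 54.8% | 27.4 |
| 0.25 | 0.620 | 38.0% | 19.0 |

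The base is up to 50, because the safety set is all dosed patients and not the 40 evaluable for efficacy.

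**3. Sensitivity to the curve.** With a Weibull shape k, the share is 1 − p^((2.07/6)^k). For k = 0.75 it is about 46% to 65%, and for k = 2 about 15% to 24%. Stops for toxicity would add to these shares. Treatment beyond progression would reduce them.

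**4. Effect on the reported rate.** Let f be the share with no post-baseline TSH and h the rate of undetected, symptom-free hypothyroidism in that group. The all-dosed rate is then too low by f × h. At f = 0.38 to 0.55, each 10 points of h costs 3.8 to 5.5 points, and nothing is lost if h = 0. The documents do not give h, so the size cannot be settled. Only part of the loss could be recovered at D30, because some of these patients will have died.

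**5. Recording at D30.** The visit may fall on any of days 30 to 37. Section 11.2.1 stops AE recording at day 30 or at new therapy, but the calendar schedules AE review at that visit. The two can be read together if the limit refers to when an event occurs, but the text does not say so.

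**The case against.** The strongest reply is that clinically relevant cases are already covered. Physical examination and AE review occur at every cycle and at the safety visit, Table 1 asks for monitoring of thyroid signs and symptoms, and an unscheduled TSH is always possible. This stands, and it confines the gap to symptom-free cases.

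Nothing in the plan turns on the figure: there is no hypothyroidism endpoint, threshold or toxicity stopping rule, and Table 1 continues pembrolizumab at Grades 2 to 4. This also stands. In addition, Section 11.1.1 does not say whether an isolated TSH change without symptoms is an AE, and the under-count presumes that it would be recorded as one.

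Test frequency is a clinical choice, and urine protein has no D30 mark either. That is fair, but urine protein is due every 9 weeks, so it coincides with the first scan, whereas TSH comes three weeks after it.

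Three stronger readings are tempting and not supported:
- A reader might infer that AE recording has closed on 7 of the 8 permitted visit days (31 to 37). The AE mark in the safety follow-up column points the other way. This is an ambiguity to clear up, and it applies to every D30 laboratory test.
- A reader might infer that a true 43% would be reported as 19% to 27% (0.43 × 0.452 and 0.43 × 0.620). That needs no case at all to be found among untested patients. It also treats a rate from other tumors, with no stated testing schedule or onset time, as the true rate here.
- A reader might want a count of patients whom a D30 test would recover. That depends on assumed curve shapes, death rates and uptake of new therapy, and the result runs from 0 to 21 of 40. It does not establish an effect.

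**Conclusion.** The scheduling gap follows from the text alone: stopping before week 12 means no scheduled TSH after baseline, with no change to the denominator. The share affected is illustratively 38% to 55% by week 9, and about 15% to 65% over the Weibull shapes tried. These figures rest on the design's hypothesised rPFS rates and on treatment stops tracking rPFS events. The likely consequence is some under-reporting of symptom-free hypothyroidism, of a size the documents do not allow anyone to state. Severity is minor, but the change is worth making because it costs so little.

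**What to change.** - Mark TSH in the D30 column of the Section 7 calendar and in footnote 3, using the blood already drawn at that visit.
- Add one sentence to Section 11.2.1: a thyroid abnormality found at the safety visit (days 30 to 37) is recorded as an AE.
- In the safety table, show the number of patients with at least one post-baseline TSH beside the all-treated hypothyroidism rate. Any rate among tested patients should be supplementary only, since it favours patients treated longer or tested because of symptoms.

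The cost is one assay per patient, one calendar mark, one sentence and one number in a table. No extra visit is needed.

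Limits: the test does not reach patients who die or are lost before D30. A lenvatinib effect may also have resolved by then: at the 28-hour half-life the protocol quotes, 30 days is 30 × 24 / 28 = 25.7 half-lives. A TSH at Cycle 3 or Cycle 4 Day 1 would test patients while on drug, but would miss those who stop earlier. It could be added if the investigators want on-treatment detection.
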